**Synopsis**

Device Names	Pivot Breath Sensor
Protocol Title	Pivot Breath Sensor Study [REDACTED]
Principal Investigator	[REDACTED]
Co-Investigators	[REDACTED]
Protocol Number	[REDACTED]
Protocol Version	[REDACTED]
Sponsor	Carrot Inc., [REDACTED]
Study Design	Prospective open label, single center study enrolling up to 220 participants to evaluate the effect of the Pivot Breath Sensor on a user's attitudes towards quitting smoking and smoking behavior.
Primary Objective	The primary objective is to collect the following data during and after use of a personal carbon monoxide breath sensor (Pivot Breath Sensor): 
 
• Change in attitudes towards quitting smoking
 
• Change in smoking behavior (quit attempts, cigarettes smoked per day)
 
• Participant feedback
 

Potential Subjects	Up to 220 subjects, comprising 2 cohorts: 
 
• 40-60% of participants who self-report smoking 10-19 cigarettes per day
 
 AND 
 
• 40-60% of participants who self-report smoking 20 or more cigarettes per day
 

Inclusion Criteria	
 
• 18-80 years of age
 
• Current daily cigarette smokers (at least 10 cigarettes per day)
 
• Resident of the United States
 
• Able to read and comprehend English
 
• Owns and uses a smartphone compatible with the study app (iPhone 5 and above with operating system iOS 11 and above, or, Android 5.0 and above with operating system Android 5.0 and above)
 
• Willing to sign the Informed Consent Form
 

Exclusion Criteria	
 
• Pregnancy
 
• Participation in a previous study sponsored by Carrot Inc.
 

Recruitment	Eligible subjects will be identified via web media (e.g., Facebook, Google ads) or via a clinical research recruiter.
Study Session	This is a prospective open-label sensor-only study conducted with IRB approval enrolling up to 220 subjects who report daily smoking of 10 cigarettes or more. The study will be performed remotely on an ambulatory basis. The subject will be asked to setup the Pivot Breath Sensor and provide

	breath samples for the 84-day duration of the study. Subjects will receive questionnaires at intervals throughout the study.
Data Collection	Data will be collected through an application (app) that the study participants install on their smartphone (the Sensor-Only app) and through participant completion of emailed online questionnaires.
Performance Variable	Assessment of the role of the Pivot Breath Sensor in attitudes towards quitting smoking and in smoking behavior: 

• Attitudes towards quitting: Stage of Change, desire to quit, confidence to quit, and difficulty to quit.

• Smoking behavior: quit attempts, change in cigarettes per day (CPD), smoking cessation via 7-and 30-day point prevalence abstinence.

• Participant feedback on the set-up, use experience, impact and commercialization of Pivot Breath Sensor.

Performance Endpoint and Analysis	Change from baseline measurement

**1. LIST OF ABBREVIATIONS**

CO	Carbon Monoxide
CPD	Cigarettes Per Day
CRF	Case Report Form
USB	Universal Serial Bus
IRB	Institutional Review Board
ICF	Informed Consent Form
HCP	Health Care Provider
ppm	parts per million

## 2. INTRODUCTION

### 2.1 BACKGROUND

The smoking of tobacco products is a leading cause of preventable morbidity and mortality, excess health care expenditure, and lost work productivity. [REDACTED]

[REDACTED]

[REDACTED]

[REDACTED]

[REDACTED]

## 2.3 POTENTIAL RISKS AND BENEFITS

### 2.3.1 Known Potential Risks

There are minimal anticipated risks or harms to the participant. Risks include breach of confidentiality should a data breach occur, and participant anxiety related to using the Pivot Breath Sensor multiple times a day. We, the study sponsor (Carrot Inc.) comply with HIPAA and state this in our privacy and terms of use on our website. As such, we adhere to HIPAA's Breach Notification Rule should a data breach occur. We take careful measures to prevent a data breach including use of encryptions, secure connections, and limited access to data (see section 10.1 "Data Collection and Confidentiality"). Regarding the risk of participant anxiety related to using the device multiple times a day, while there are suggested breath sampling patterns provided during the screening call and with the breath sensor, participants will ultimately sample at their discretion. No medical decisions are made based on study data.

### 2.3.2 Known Potential Benefits

While we do not anticipate that participants will receive any benefit from their participation in this study, it is possible that some participants may experience an increased awareness of their smoking behavior. It is possible this awareness and new information on how much carbon monoxide is in their body may help a participant quit smoking.

### 2.3.3 Risk Benefit Assessment

Given the non-invasive nature of the breath sampling and the data collection, there are minimal anticipated risks. These risks relate to breach of confidentiality in the circumstance of a data breach, and possible participant anxiety related to using the Pivot Breath Sensor multiple times a day. These risks have been mitigated to the extent possible through data protection measures and through enabling participants to ultimately decide if and when they do breath samples. Participants will have the remote support of study staff and customer support as they need over the course of the study. Participants are not asked to change their smoking behavior. No medical decisions are made based on study data.

## 3. OBJECTIVES

We aim to measure participants' use of the Pivot Breath Sensor (Pivot Breath Sensor, Carrot Inc.; Redwood City, CA, USA; 510(k) number: K171408) and to non-invasively measure their carbon monoxide (CO) levels in their exhaled breath. There will be a focus to assess changes in attitudes towards quitting smoking and changes in smoking behavior over the course of the 84-day study, as well as participant feedback on the set-up, use experience, impact and commercialization of the Pivot Breath Sensor.

#### 4. DEFINITIONS

Bluetooth Low Energy (BLE): a global wireless communication standard that connects devices together over a certain distance.

Data: Data collected through the Pivot Breath Sensor, Sensor-Only app and participant-completed online email questionnaires

Pivot Breath Sensor: The study device; a personal mobile breath sensor that is capable of measuring the level of carbon monoxide (CO) in exhaled breath. It is portable, battery-powered, and small enough to be carried by the user throughout the day (pocket, purse, backpack). The sensor is intended for single-user use by cigarette smokers to inform the user about how breath carbon monoxide levels are affected by smoking behavior. The user submits a breath sample by exhaling (blowing) directly into the mouthpiece connected to the sensor with breath sample results displayed on a screen on the sensor.

User: Person who interacts with (i.e., operates or handles) the Pivot Breath Sensor.

Sensor-Only app: App installed on user’s smartphone. User’s smartphone is connected to the Pivot Breath Sensor via BLE. Participant breath sensor usage data and carbon monoxide results populate the Sensor-Only app and are available to the study team in real-time.

#### 5. DEVICE DESCRIPTION

##### 5.1 PIVOT BREATH SENSOR, STUDY DEVICE

The Pivot Breath Sensor comprises a personal mobile breath sensor that measures the level of CO in exhaled breath and displays the exhaled breath CO value to the user directly on the device. The range of CO measurement is 0-100 ppm.

The Pivot Breath Sensor (Figure 1) is portable, battery-powered, and small enough to be conveniently carried by the user throughout the day (pocket, purse, backpack). The Pivot Breath Sensor is rechargeable using a micro-USB cable. The user submits a breath sample by exhaling (blowing) into the mouthpiece of the Pivot Breath Sensor.

##### 5.1.1 Indications for Use

*The Pivot Breath Sensor is a breath carbon monoxide monitor intended for single-user use by cigarette smokers to inform the user about how breath carbon monoxide levels are affected by smoking behavior. The device is not intended to be used with other inhaled products.*

**Figure 1. Pivot Breath Sensor**

## **5.2 LABELING AND PACKAGING**

The Pivot Breath Sensor package includes:

- 1 Pivot Breath Sensor
- 1 USB charging cable
- 1 Replaceable Mouthpiece
- 1 Quick Start Guide [REDACTED]
- 1 Packaging Insert [REDACTED]

The Pivot Breath Sensor packaging is shown in [REDACTED]

## **5.3 PIVOT BREATH SENSOR SUBMITTING A BREATH SAMPLE (SPECIFIC STEPS)**

Submitting a breath sample involves the following steps. Instructions can be accessed in multiple locations including the Pivot Sensor's display screen, in the online User Manual [REDACTED] Quick Start Guide, and on the packaging.

1. User presses any button to turn on the Pivot Breath Sensor.
2. User presses and holds the center button on the Pivot Breath Sensor until the sensor beeps once.
3. User takes a deep breath in and holds their breath for 10 seconds.
4. After about 10 seconds, the device beeps 3 times, and the user then will exhale slowly until the sensor vibrates at 12 seconds.
5. The user's CO level will display on the sensor's screen.

A properly submitted breath sample is defined as one that initiates after the third beep prompt and is of at least 6 seconds duration. Breath sensor hardware and firmware is capable of detecting when a breath sample submission starts and stops.

The CO Log screen on the Pivot Breath Sensor provides the CO (ppm) value for properly submitted breath samples.

The computation of concentration of CO (ppm) is performed within the Pivot Breath Sensor firmware and the data (CO ppm concentration, time and date) are stored in the Pivot Breath Sensor memory. This data is also stored in the Sensor-Only app when the

Pivot Breath Sensor and user's smartphone app are paired. Opening the app syncs the data to its most updated state, which study staff may access in real-time. User's may also sync their breath sensor data by tapping the breath sensor icon in the upper right corner of the app and then tapping "Sync Now" in the dropdown menu.

#### 5.4 CO LOG

The CO Log can be accessed from the Pivot Breath Sensor's display screen and shows the most recent exhaled breath CO value in ppm at the top of the screen. The user can view previous values by scrolling within the log (Figure 3).

Values are color coded and can be interpreted by the user with help from the labeling (Figure 4).

**Figure 3. CO log on Pivot Breath Sensor**

**Figure 4. Package labeling to interpret results**

## How to interpret your CO sample

Remember: no amount of smoking is safe

Each of your breath sample results is displayed on the sensor screen with a color and a number and are measured in parts per million (ppm).

If you are a smoker, you may also obtain a green or orange reading if you have not smoked for an extended period of time.

CO values are also stored in the Sensor-Only app on the participant's smartphone. When the Pivot Breath Sensor is paired to a user's phone, his/her CO values, date/time of breath samples, and any error codes populate the Sensor-Only app; this data is accessible to study staff in real-time but is not visible to study participants.

## 6. STUDY DESIGN AND OVERVIEW

### 6.1 STUDY DESIGN

This is a prospective open-label sensor-only study conducted with IRB approval enrolling up to 220 subjects who report daily smoking of 10 cigarettes or more. The study will be performed remotely on an ambulatory basis. The participant will be asked to setup the Pivot Breath Sensor and participate for 84 days with an emphasis on providing breath samples and completing online study questionnaires. The suggested breath sampling regimen is at least 4 breath samples per day, spread over the course of the day. Participants will receive the online questionnaires via email at intervals throughout the study.

### 6.2 STUDY DURATION

The study will run for 84 days (+ up to 14 days to obtain completion of the final questionnaire), with questionnaires emailed at baseline, 7, 14, 21, 28, 56 and 84 days.

### 6.3 STUDY OUTCOMES

- Attitudes towards quitting: Stage of Change, desire to quit, confidence to quit, difficulty to quit, goals
- Smoking behavior: quit attempts, change in cigarettes per day (CPD), smoking cessation via 7- and 30-day point prevalence abstinence.
- Participant feedback on the set-up, use experience, impact and commercialization of the

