### **7.5 DAYS 1 THROUGH 84 – STUDY QUESTIONNAIRES**

Participants will receive periodic electronic questionnaires via email (Survey Monkey) that focus on attitudes towards quitting, smoking behavior, and participant feedback on breath sensor set-up, user experience, impact and commercialization (Section 7.7).

Participants will receive periodic reminders from study staff to complete the questionnaires via email, text or phone, as needed. All participants will receive the 28-day and 84-day questionnaires, regardless of previous completion of questionnaires.

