**7.7 SCHEDULE OF STUDY ACTIVITIES**

Event	Screening 	Registration	1	7	14	21	28	56	84	84-98
Eligibility confirmed	X									
Phone call	X		X 							
Informed consent		X								
Receive breath sensor 			X							
Active use of breath sensor			X	X	X	X	X	X	X	
Survey		X		X	X	X	X	X	X	
- Baseline and demographic data		X								
- Access device settings				X	X	X	X	X	X	
- Feedback: breath sensor set-up				X						
- CPD		X		X	X	X	X	X	X	
- Desire to quit		X		X	X		X	X	X	
- Difficulty to stay quit		X		X	X		X	X	X	
- Stage of Change		X		X	X		X	X	X	
- Readiness to quit		X		X	X		X	X	X	
- Confidence to quit		X		X	X		X	X	X	
- Goals		X		X	X		X	X	X	
- Point prevalence abstinence					X	X	X	X	X	
- Quit attempts		X			X		X	X	X	
- CO reading understanding				X	X		X	X	X	
- Feedback: breath sensor experience and use				X	X		X	X	X	
- Feedback: impact of breath sensor				X	X	X	X			
- Feedback: commercialization					X		X			
Final questionnaire										X
Return breath sensor										X
Study completion										X

1 Screening is a phone call to prescreened candidates based on their responses to an online screening questionnaire.

2 Pivot Breath Sensor received by participant only after confirmation of eligibility and provision of electronic informed consent.

3 Optional phone call to assist with breath sensor set-up as needed

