## 10. STUDY RESULTS

### 10.1 DATA COLLECTION AND CONFIDENTIALITY

Participants will be assigned a unique participant ID which will be used for data collection. Data collection will take place on electronic case report forms (CRFs)

completed by study participants and through data collected in the Sensor-Only app (participant breath sensor usage and CO values of breath samples). CRFs will be reviewed by the study team prior to the end of the study to ensure completeness. Access to electronic CRFs will be limited to necessary study personnel. Study data will be kept in a secure database by the investigator. This database will be accessible only by necessary study personnel. The database will not contain personal identifying information; all subject data in the database will be associated with study identification numbers. The data will be kept for a minimum of 5 years. The data shall be retained for a maximum period of time that is equivalent to the design and expected life of the Pivot Breath Sensor device or the duration of the study sponsor's (Carrot Inc.) existence, whichever is the shortest of the two.

Data on the breath sensor will be accessed with an app customized for this study. This Sensor-only app is our commercially available app with select function disabled. The app to be used in this study will request location permissions in order to complete the Bluetooth scanning and pairing process with the sensor. Other features to access functionality (e.g camera, microphone) are disabled for this study. With regard to the information we will collect, we, the study sponsor, associate each logged in user to a user Id that is a unique identifier which is generated randomly on account creation. We will periodically synchronize logs from the sensor and upload them based on this user\_Id only. The breath samples we collect only contain information regarding: Sample Id, Sample Type, SampleValue, Sample Time. When we upload this information, the only additional information included would be the App build information and user's Sensor ID. We comply with HIPAA and state this in our privacy and terms of use on our website. As such we adhere to HIPAA's Breach Notification Rule should a data breach occur. We take careful measures to prevent a data breach including use of encryptions, secure connections, and limited access to data.

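### Abstinence is taken from questionnaires alone, and no planned analysis sets it against the dated CO readings collected from the same participants

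*Combined protocol and SAP*

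**What the plan says.** **Outcome.** Section 6.3 includes "smoking cessation via 7- and 30-day point prevalence abstinence" under smoking behaviour, as does the synopsis. The primary endpoint in 6.3 is change in Stage of Change at day 28. The two named secondary endpoints are quit attempts and a reduction of at least 50% in cigarettes per day (CPD).

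**Source.** The schedule in 7.7 lists "Point prevalence abstinence" under the survey row at days 14, 21, 28, 56 and 84. Section 7.5 describes the instrument: "Participants will receive periodic electronic questionnaires via email (Survey Monkey) that focus on attitudes towards quitting, smoking behavior, and participant feedback". No CO criterion is attached to abstinence in the available text.

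**CO data.** Section 3 gives one aim as "to non-invasively measure their carbon monoxide (CO) levels in their exhaled breath". Section 5.3 says "the data (CO ppm concentration, time and date) are stored in the Pivot Breath Sensor memory", and 5.4 adds of the synced values that "this data is accessible to study staff in real-time but is not visible to study participants". Section 10.1 names "participant breath sensor usage and CO values of breath samples" among the data collected. On frequency, 6.1 states: "The suggested breath sampling regimen is at least 4 breath samples per day, spread over the course of the day". Section 7.4 leaves actual use to the participant.

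**Analysis and report.** Section 10.2 names attitudes and CPD for the longitudinal model and bases completer analyses on survey response. It does not mention CO. Section 10.3 promises a report of sensor usage but does not mention CO values.

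**The concern.** Participants are their own controls (10.2), so no comparison arm would absorb over-reporting of abstinence. The investigators hold equity in the device company (Section 11), which makes an objective check more useful to a sceptical reader. Readings that could expose a false report will already be in the database. Under the plan as written they cannot alter the abstinence result, even where they plainly disagree with it.

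The carry-forward rule adds to this. A report of abstinence at day 14 or 21 becomes the day-28 result if the participant then stops answering, whatever the sensor recorded afterwards. At stake is the credibility of the reported quit rate, not the primary result.

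**Working it through.** No stated figure needs reproducing, because the plan gives no expected rate or sample size for abstinence. The sample sizes in 6.6 (50, 16 and 185) concern Stage of Change, quit attempts and CPD reduction. The check is therefore a comparison of sections, plus a count of which look-back windows the sensor can cover.

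**1. Are both measures held on the same people?** Yes. Enrolment requires a paired sensor, a first breath sample and the Baseline Questionnaire (6.4, 7.3). Abstinence comes from the later questionnaires (7.5, 7.7), and CO comes from the sensor through the app (5.3, 5.4, 10.1).

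**2. Does any planned analysis join them?** No. Section 10.2 has a general statement about assessing change in measurements, but gives no CO summary, time window, cut-off or rule for disagreement with self-report.

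**3. Which windows can the sensor cover?** Sensor use starts on Day 1 (7.3) and is scheduled to day 84 (7.7). For a questionnaire completed on day d, take the window as days d−7 to d−1 or d−30 to d−1.

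| Completed on day | 7-day window | 30-day window | 30-day window wholly after Day 1? |
|---|---|---|---|
| 14 | 7 to 13 | −16 to 13 | No |
| 21 | 14 to 20 | −9 to 20 | No |
| 28 | 21 to 27 | −2 to 27 | No |
| 56 | 49 to 55 | 26 to 55 | Yes |
| 84 | 77 to 83 | 54 to 83 | Yes |
| 98 (latest final questionnaire, 7.6) | 91 to 97 | 68 to 97 | Yes, but days 85 to 97 (13 of 30) fall after scheduled use |

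The 7-day check is possible at all five scheduled timepoints. The 30-day check is possible only at days 56 and 84. A final questionnaire completed on day 98 has its whole 7-day window, and 13 of its 30 days, outside scheduled sensor use. The window must therefore follow the completion date, and participants without readings need their own category.

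**4. How many readings per window?** At the suggested rate, 4 × 7 = 28 readings in 7 days and 4 × 30 = 120 in 30 days. These are suggested numbers only, since sampling is discretionary and values reach staff only after a sync.

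**5. What can a reading show?** A smoker-range reading can contradict a claim of abstinence. A low reading cannot confirm one: the label text in 5.4 says smokers may also obtain green or orange readings after an extended time without smoking, and participants choose when to sample.

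**6. Size.** No abstinence rate or discordance rate is given. Purely as an illustration, assume 5 to 10% of 220 report abstinence (220 × 0.05 = 11; 220 × 0.10 = 22) and 10 to 30% of those have contradicting readings. Then 11 × 0.10 = 1.1 to 22 × 0.30 = 6.6 people change class, which is 1.1/220 = 0.5 to 6.6/220 = 3.0 percentage points. Both inputs are assumed, so this range shows scale only and is not an estimate.

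**The case against.** The best case against acting is that abstinence is a listed outcome without a hypothesis or sample size, so no powered endpoint moves. That stands, and it limits the weight of the point. Section 3 puts its focus on attitudes, behaviour and feedback, and the synopsis objective contains no CO outcome. The general wording in 10.2 does not exclude CO. That also stands: a reader might infer that the plan fails a stated CO objective, but the documents show only that CO is measured and left without a specified analysis.

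Four other stronger readings are tempting and are not supported:

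- **That every error pushes the quit rate up.** Payment in 6.5 is for giving samples, completing questionnaires and returning the device, not for particular answers. Participants are not asked to change their smoking (2.3.3). Where nothing can be carried forward, 10.2 counts the participant as unchanged from baseline, which for enrolled daily smokers means still smoking.
- **That the readings cover the look-back periods.** The table above shows that several windows are not covered.
- **That a single smoker-range reading should reclassify a participant.** With up to about 120 unsupervised readings in 30 days, one value from another inhaled product or another user could overturn a true report. The chance of contradiction also rises with sampling frequency, so diligent samplers would be penalised.
- **That mean CO corroborates CPD change.** Sampling times are self-chosen, so this evidence is weak.

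The questionnaire wording is not in the available text, so self-report is inferred from 7.5 and 7.7. None of this answers the central point that dated readings able to contradict a claim of abstinence are collected and not used.

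**Conclusion.** The concern holds in a limited form. Abstinence rests on questionnaires alone, contradicting evidence is collected for the same people, and no planned analysis uses it. The primary endpoint, the two named secondary endpoints and all stated sample sizes are unaffected. The size of the effect on the quit rate cannot be estimated from the documents. The conclusion assumes that the abstinence items are self-reported, as the schedule and 7.5 indicate, and that the redacted material contains no CO criterion. It is a worthwhile, low-cost improvement to a supporting outcome, and does not show that the reported quit rate will be wrong.

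**What to change.** Add to Section 10.2, before the data are analysed:

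- Keep self-reported abstinence as the main figure, and add one sensitivity analysis: self-reported abstinence not contradicted by CO.
- Anchor each window to the questionnaire completion date. Use 7-day abstinence at days 14, 21, 28, 56 and 84, and 30-day abstinence only at days 56 and 84.
- Take the smoker-range cut-off from the sponsor's own device label and state it in the plan. The limits are not in the available text, so none is suggested here.
- Use CO only to contradict, never to confirm.
- Report three groups of self-reported abstainers (contradicted, not contradicted, no reading in the window), with the number of readings per person.
- Show the result under two rules, any smoker-range reading and smoker-range readings on more than one day, and flag participants who report other inhaled products (collected under Section 8).
- Apply the same check to abstinence answers carried forward to day 28 or day 84. These have no completion date at the target visit, so end the window on the target day.
- Summarise CO by visit window descriptively only.

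The cost is modest analysis work on data already held, with no change to sample size or procedures. The downsides are a possibly lower quit rate in the sensitivity analysis and some misclassification from other CO sources or uneven sampling, which the two rules and the reading counts make visible.
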